### Treatment-Emergent Vital Sign Abnormalities

The treatment policy strategy will be applied for estimating the incidence of treatment-emergent vital sign abnormalities. Vital sign abnormalities recorded since receiving the first dose of investigational medication until EOS will be presented regardless of any potential intercurrent events. Vital sign abnormalities that are absent at baseline will be considered treatment-emergent.

The overall incidence of treatment-emergent vital sign abnormalities will be summarized at event level and subject level by test item.

## **6.8.2. Secondary Analysis Supporting Secondary Objectives**

### Overall Response

Achievement of response will be assessed after the database lock via a programmed algorithm. The derivation of the Overall Response is detailed below.

Overall Response		
Response	Definition	Additional Clarifications
Complete Response	Complete Response is adjudicated if: 
 
- No fever = body temperature <37.5°C
 
- Normal spleen size
 
- No cytopenia = Absolute Neutrophil Counts <math>\geq 1.0 \times 10^9/L</math> and platelet count <math>\geq 100 \times 10^9/L</math> [absence of G-CSF and transfusion support must be documented for at least 4 days to report no cytopenia]
 
- No hyperferritinemia = serum ferritin level is <2000 <math>\mu g/L</math>
 
- No evidence of coagulopathy, i.e., normal D-Dimer and/or normal (>150 mg/dL) fibrinogen levels
 
- No neurological and CSF abnormalities attributed to HLH
 
- No sustained worsening of sCD25 (as indicated by at least two consecutive measurements that are > 2-fold higher than baseline)
 
	
 
- All HLH parameters that were abnormal at baseline must be normalized
 
- No AEs relating to organ failure
 
- All other parameters that were normal at baseline must still meet the definition of normalized
 
- Normal spleen size confirmed by abdominal ultrasound (US) whenever possible based on the splenomegaly not present; if US not performed physical examination will be used
 
- Normal D-Dimer levels are <math>\leq 500 \mu g/L</math>
 
- No neurological abnormalities attributed to HLH = “normal” neurological assessment by investigator in the neurological examination page (without findings in brain imaging (Brain MRI/Brain CT/cranial ultrasound) or AEs indicative of “CNS involvement”
 
- No CSF abnormalities = no AE indicative of “CSF abnormalities”
 

Partial Response	Partial Response is adjudicated if: 
 
- At least 3 of the HLH clinical and laboratory abnormalities (including CNS abnormalities) meet
 
	If a patient is not considered as “reactivated” or a patient is considered “reactivated” with 4 or more abnormal HLH features upon entry to the study and

	
the above mentioned criteria for “Complete Response”
 
 
- In the case of “reactivated patients” who enter the study with 3 abnormal HLH features, Partial Response is adjudicated if at least 2 parameters normalize
 
- In case of reactivated patients who enter the study with 2 abnormal HLH clinical and laboratory parameters only, Partial Response is adjudicated if one of the 2 parameters normalizes
 
- There is no progression of other aspects of HLH disease pathology
 
	
at least 3 of the HLH clinical and laboratory abnormalities (including CNS abnormalities) meet the above-mentioned criteria for “Complete Response” Partial Response is adjudicated.
 
For all patients: no progression of other aspects of HLH disease pathology is assessed by absence of AEs indicating organ failure including no worsening of sCD25 levels.

HLH improvement	
HLH Improvement is adjudicated if:
 
 
- Improvement (>50% change from baseline or normalization) of at least 3 HLH clinical and laboratory abnormalities (including CNS abnormalities).
 
- In the case of “reactivated patients” who enter the study with only 2 abnormal HLH features, a change from baseline greater than 50% for both will define HLH as improved.
 
	
Definition of 50% improvement from baseline:
 
 
- Spleen size decreased by 50%, as recorded in cm from costal margin at physical examination.
 
- Absolute Neutrophil Count increased by 50%, if G-CSF has not been administered in the previous 4 days and Platelet count increased by 50%, if no platelet transfusion has been administered in the previous 4 days
 
- Ferritin decreased by 50%
 
- Fibrinogen increased by 50% or D-Dimer decreased by 50%
 
 
Normalization of CNS abnormalities = normal neurological assessment by investigator without findings in brain imaging (Brain MRI/Brain CT/cranial ultrasound), CSF analysis or AEs indicative of “CNS involvement” or “CSF abnormalities”

No Response	
If a subject does not meet the criteria for at least HLH improvement, response is categorized as “No Response”
	

Abbreviations: CNS, central nervous system; CSF, cerebrospinal fluid; G-CSF, granulocyte-colony-stimulating factor; HLH, hemophagocytic lymphohistiocytosis
		

 AE indicating organ failures will be pre-specified according to [Appendix 1](#).

 AE indicative of CNS involvement/CSF abnormalities will be pre-specified according to [Appendix 2](#).

The treatment policy strategy will be applied. The achievement of response based on the above definition at EOT or week 8 will be estimated as described below regardless of any potential intercurrent events.

Subjects who failed to meet the definition for above categories (Complete Response, Partial Response or HLH Improvement) will be considered as No Response. The number and percentage of patients achieving Overall Response at EOT or week 8 (whichever occurs earlier), i.e., Complete Response or Partial Response or HLH improvement, as well as No Response will be provided. In addition, 95% confidence interval will be estimated using Clopper-Pearson exact method for the percentages of subjects achieving each Overall Response category. Subjects’ response status and assessments corresponding to each response criterion will be listed.

For subjects that did not withdraw treatment before week 8, observed data from the visit closest to 56 days (8 weeks) after first infusion will be used in the analysis. If there are more than one visits that are the same distance from 56 days after first infusion, data from the earlier/earliest visit will be used.

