6.3.1 Inclusion criteria

A patient must fulfill the following criteria in order to be included in the study:

1. Male and female HLH patients of any age.
2. Patients diagnosed with confirmed or suspected pHLH, based on; a molecular diagnosis or familial history consistent with pHLH or fulfilment of HLH-2004 diagnostic criteria, i.e., five out of eight of the criteria below:

- Fever
 - Splenomegaly
 - Cytopenias affecting 2 of 3 lineages in the peripheral blood (hemoglobin <90 g/L; platelets <100 x 10⁹/L; neutrophils <1 x 10⁹/L)
 - Hypertriglyceridemia (fasting triglycerides ≥3 mmol/L or ≥265 mg/dL) and/or hypofibrinogenemia (≤1.5 g/L)
 - Hemophagocytosis in bone marrow, spleen, or lymph nodes, with no evidence of malignancy.
 - Low or absent NK-cell activity ⁱ
 - Ferritin ≥500 µg/L
 - Soluble CD25 (sCD25; i.e., soluble IL-2 receptor) ≥2400 U/mL ⁱⁱ
3. Presence of active HLH disease as assessed by the investigator.
 4. Patients must fulfil one of the following criteria as assessed by the investigator:
 - Having not responded to previous conventional treatment of HLH
 - Having not achieved a satisfactory response to previous conventional treatment of HLH or worsened
 - Having reactivated ⁱⁱⁱ
 - Showing intolerance to previous conventional treatment of HLH
- At the time of enrollment, eligible patients might still be receiving treatment (induction or maintenance) or might have already discontinued it.
5. Expectation of survival beyond 1 week as judged by the investigator.
 6. Patient has expectation of proceeding to HSCT
 7. Informed consent signed by the patient (as required by local law), or by the patient's legally authorized representative(s) with the assent of patients who are legally capable of providing it, as applicable.
 8. Willing to use highly effective methods of contraception from study drug initiation to 6 months after the last dose of study drug, if female and of childbearing potential.

In case of use of oral contraception women should have been stable on the same brand (or generic equivalent) for a minimum of 3 months before taking study treatment. Women are considered post-menopausal and not of childbearing potential if they have had 12 months of natural (spontaneous) amenorrhea with an appropriate clinical profile (e.g., age appropriate, history of vasomotor symptoms) or have had surgical bilateral oophorectomy (with or without hysterectomy) or tubal ligation at least six weeks ago.

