6.5.4 Efficacy endpoints assessments

6.5.4.1 Overall Response

Overall Response is defined as achievement of either Complete or Partial Response or HLH Improvement, at EOT or week 8 (whichever occurs earlier).

Complete response, partial response and HLH improvement and time to first response will be assessed after the database lock via a programmed algorithm, based on the Table 5 below.

Table 5 Definition of response

Overall Response	
Complete Response	Complete Response is adjudicated if:

	
 - No fever = body temperature <37.5°C - Normal spleen size - No cytopenia = Absolute Neutrophil Counts $\geq 1.0 \times 10^9/L$ and platelet count $\geq 100 \times 10^9/L$ [absence of G-CSF and transfusion support must be documented for at least 4 days to report no cytopenia] - No hyperferritinemia = serum level is <2000 µg/L - No evidence of coagulopathy, i.e., normal D-Dimer and/or normal (>150 mg/dL) fibrinogen levels - No neurological and CSF abnormalities attributed to HLH - No sustained worsening of sCD25 (as indicated by at least two consecutive measurements that are > 2-fold higher than baseline)
Partial Response	
Partial Response is adjudicated if:
 
 - At least 3 of the HLH clinical and laboratory abnormalities (including CNS abnormalities) meet the above-mentioned criteria for "Complete Response" - In the case of "reactivated patients" who enter the study with 3 abnormal HLH features, Partial Response is adjudicated if at least 2 parameters normalize - In case of reactivated patients who enter the study with 2 abnormal HLH clinical and laboratory parameters only, Partial Response is adjudicated if one of the 2 parameters normalizes - There is no progression of other aspects of HLH disease pathology
HLH improvement	
 - Improvement (>50% change from baseline or normalization) of at least 3 HLH clinical and laboratory abnormalities (including CNS abnormalities). - In the case of "reactivated patients" who enter the study with only 2 abnormal HLH features, a change from baseline greater than 50% for both will define HLH as improved.

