Baseline will be defined as the last available measurement or recording prior to the first study drug administration. For assessments performed only on screening visit prior to the first emapalumab infusion, the measurement or the recording of the screening visit will be used as baseline. For

assessments that are also performed pre-infusion on visit 1 in addition to screening visit, the measurement or recording pre-infusion on visit 1 will be used. If the measurement or recording pre-infusion on visit 1 is not available, then the measurement or recording of the screening visit will be used.

Unless otherwise noted, descriptive statistical summary will only include data from scheduled visits or time points. Data from unscheduled visits or time points will be presented in data listings. For data of quantitative measurements but are collected with characters such as “>/≥” or “</≤”, the numeric part of the value will be used in the descriptive analysis. For other cases where characters are entered for quantitative measurements, the result will not be used in the descriptive analysis but only included in data listing.

If deemed necessary, specific data points may be excluded from the analysis based on related discussion in the data review meeting (DRM). The decisions and reason(s) for exclusion will be documented separately in Resolution of Data Review Meeting in detail.

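### The Complete Response rule requires no abnormality at baseline, so a patient who already meets every line before the first infusion and does not change is counted as a Complete Response

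*SAP*

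**What the plan says.** **Entry (Protocol 6.3.1).** Criterion 2 offers alternative routes: "a molecular diagnosis or familial history consistent with pHLH or fulfilment of HLH-2004 diagnostic criteria", the last meaning five of eight items. One of the eight is "Ferritin ≥500 µg/L". Criterion 3 is "Presence of active HLH disease as assessed by the investigator", with no numeric content. Criterion 4 requires no or inadequate response, worsening, reactivation or intolerance, again as judged by the investigator. Only reactivation has numeric rules (note iii).

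**Response (Protocol 6.5.4.1, Table 5; SAP 6.8.2).** Complete Response has its own items and cut-offs, for example "No hyperferritinemia = serum level is <2000 µg/L". The SAP's clarification column adds "All HLH parameters that were abnormal at baseline must be normalized", that parameters normal at baseline must remain so, and that there be no organ-failure adverse event. Partial Response and HLH Improvement are built on counts of abnormal features. Complete Response is not.

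**Baseline (SAP 6.1).** "Baseline will be defined as the last available measurement or recording prior to the first study drug administration".

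**Population and modified definition.** All treated patients are analysed (SAP 5). The supplementary definition in SAP 6.12 changes Partial Response and HLH Improvement but repeats the Complete Response row.

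**The concern.** Both clarifications are conditional: they say what must happen to parameters that were abnormal and to those that were normal. If no response-table parameter is abnormal at baseline, the first condition is met with nothing to check and the second is met by staying the same. A programmed algorithm that follows the text returns Complete Response for an unchanged patient.

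This matters for three endpoints that share the definition: Overall Response, time to first response and cumulative duration. Each could credit emapalumab with a state that was present before the first infusion. SAP 9 describes the supplementary analysis as taking the number of baseline abnormalities into account, so the baseline count was recognised as relevant. But SAP 6.12 has no rule for a patient with none.

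**Working it through.** The plan derives no figure on this point, so the check is mainly logical.

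**Step 1. Set the eight HLH-2004 entry items against the Complete Response lines.** The protocol gives no temperature for fever at entry; I assume it is at least 37.5 °C.

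| Entry item (Protocol 6.3.1) | Complete Response line (Table 5, SAP 6.8.2) | Can both hold at baseline? |
|---|---|---|
| Fever | below 37.5 °C | No |
| Splenomegaly | normal spleen | No |
| Two of three lineages low | neutrophils at least 1.0 and platelets at least 100 × 10⁹/L | No: any two of hemoglobin, platelets and neutrophils include one of the last two |
| Triglycerides ≥3 mmol/L and/or fibrinogen ≤1.5 g/L | normal D-dimer and/or fibrinogen above 150 mg/dL; no triglyceride line | Yes |
| Hemophagocytosis | no line | Yes |
| Low NK-cell activity | no line | Yes |
| Ferritin ≥500 µg/L | below 2000 µg/L | Yes, from 500 to just under 2000 |
| sCD25 ≥2400 U/mL | no two consecutive values above twice baseline | Yes: always met at baseline |

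The remaining line, neurological and CSF findings, has no counterpart among the eight.

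**Step 2. Count the qualifying sets.** Sets of five from eight: C(8,5) = 56. Sets of five or more: 56 + 28 + 8 + 1 = 93. Three items block Complete Response and five do not, so exactly one set works: C(5,5) = 1. That is 1 of 56, or 1 of 93.

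**Step 3. Construct a patient.** Temperature 37.0 °C, normal spleen, platelets 120 and neutrophils 1.5 × 10⁹/L without G-CSF or transfusion, triglycerides 3.5 mmol/L, fibrinogen 180 mg/dL, D-dimer 400 µg/L, ferritin 1800 µg/L, sCD25 6000 U/mL, hemophagocytosis present, NK activity low, no CNS findings. Entry items met: 5 of 8. Complete Response lines met at baseline: all. If nothing changes by week 8, the result is Complete Response. It is still Complete Response with ferritin 1990 and sCD25 11,900, because 1990 < 2000 and 11,900 < 2 × 6000 = 12,000.

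**Step 4. The other routes.** Molecular diagnosis or family history requires none of the eight items, so the opening is wider there. Criteria 3 and 4 still apply on every route, but the algorithm does not use them.

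**Step 5. Size.** One patient counted as a responder rather than a non-responder adds 1/18 = 5.6 points or 1/10 = 10.0 points. The Clopper-Pearson calculation was checked first on the earlier study's 27/45: it gives 44.3% to 74.3%, as Protocol 4.1.1.3.2 states. The counts below are assumed, for illustration only:

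- n = 10: 4/10 = 40.0% (12.2% to 73.8%) becomes 5/10 = 50.0% (18.7% to 81.3%). With the patient left out altogether: 4/9 = 44.4%.
- n = 18: 7/18 = 38.9% (17.3% to 64.3%) becomes 8/18 = 44.4% (21.5% to 69.2%). With the patient left out altogether: 7/17 = 41.2%.

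**Step 6. Timing.** SAP 6.2.2 computes time to response as date of response minus date of first dose plus 1. If Visit 2 (SD3 or SD4) is the first visit evaluated, the value is 3 + 1 = 4 or 4 + 1 = 5 days. Cumulative duration then runs from that visit to EOT for as long as the state holds.

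**The case against.** **The case is narrow.** This stands. Only one five-item set produces it, and that patient has no fever, a normal spleen, adequate counts and no CNS findings, yet must be judged to have active disease. A reader might infer that the response rate will be inflated. The documents support only that it could be.

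**The cut-off for baseline abnormality is implied.** This largely stands. A reader might infer that ferritin of 900 µg/L before and after could be scored as abnormal and then normalised, and so supply one of the three features needed for Partial Response. The SAP requires parameters normal at baseline to go on meeting the normalisation definition, which points to the response-table limits at both times. On that reading 900 is normal throughout. The other reading is a possible misreading, best closed by a sentence; it is not an established error.

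**HLH parameters might mean every HLH-2004 item.** That would block the five-item case. But the response table sets no limit for triglycerides, NK activity, hemophagocytosis or absolute sCD25, and Protocol Table 3 schedules no repeat NK or marrow test. It would not close the molecular or family-history route either.

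**Listings would reveal such a patient.** Partly. SAP 6.8.2 lists the assessments behind each criterion, and investigator-assessed response is tabulated separately. Neither changes the tabulated rate.

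**Baseline timing.** A reader might also fault a baseline taken after dexamethasone has started. That is not a defect: a last pre-dose baseline avoids crediting emapalumab with earlier steroid effect.

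**Conclusion.** The point holds as a statement of what the written rule does: an unchanged patient with no response-table abnormality at baseline is a Complete Response under SAP 6.8.2 and 6.12. This is more than missing detail, because following the text gives that result. Each such patient could move Overall Response by 5.6 (n = 18) to 10 (n = 10) percentage points compared with being a non-responder, and would shorten time to response and lengthen cumulative duration.

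This rests on reading the response parameters as those in the response table, and on no organ-failure event or new abnormality arising. Frequency is unknown and probably low. Overall Response is secondary and descriptive, with no hypothesis test, and the primary safety endpoint is unaffected. It should be settled before the algorithm is run.

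**What to change.** In SAP 6.8.2 and 6.12:

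1. State that a parameter is abnormal at baseline if it fails its Complete Response threshold at the SAP 6.1 baseline, and that only such parameters count as normalised or improved. The sCD25 line is relative to baseline, so sCD25 can never fail it there. State separately whether it counts as an abnormal feature, at what absolute level, and, if so, what counts as its normalisation. Keep this consistent with Protocol 6.3.1 note iii, which names sCD25 as a reactivation parameter; otherwise the two- and three-feature counts for reactivated patients would shift.
2. Tabulate the number of response-table abnormalities per patient at baseline.
3. Show patients with none in a separate row (no response-table abnormality at baseline) instead of under Complete Response. Report Overall Response, time to first response and cumulative duration both for all treated patients and for those with at least one baseline abnormality. State how the separate row enters the all-treated rate: barring these patients from response while keeping them in the denominator would make them automatic non-responders, which is the opposite bias.

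The cost is SAP wording, one derived baseline variable from data already scheduled before the first infusion, and a second set of summaries. The response rate may look slightly less favourable. Eligibility and patient care do not change.

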6.5.5 Safety assessments

6.5.5.1 Adverse events

6.5.5.1.1 Definitions

Adverse event (AE)

An AE is any untoward medical occurrence in a patient or study patient administered a pharmaceutical product; the event does not necessarily have a causal relationship with the treatment or usage.

AEs include the following:

- Abnormal test findings, as specified below.
- Clinically significant signs and symptoms.
- Changes in physical examination findings.
- Progression/worsening of underlying disease.

In addition, signs and symptoms resulting from the following should also be handled according to the same principles as AEs:

- Overdose.
- Withdrawal of treatment.
- Interactions.
- Abuse.
- Misuse.

For pregnancies and breastfeeding, see 6.5.5.1.6

Abnormal test findings

An abnormal test finding, e.g. abnormal laboratory analysis results, vital signs, or ECG, should be recorded as an AE in any of the following situations:

- The investigator considers the abnormal test finding to be clinically significant.
- The abnormal test finding is associated with accompanying symptoms. Note, that the symptom, not the test result, should be recorded as an AE.
- The abnormal test finding leads to a medical/surgical intervention including withdrawal of IMP(s) or discontinuation from the study. Repeat/confirmatory testing is not considered a medical intervention.

Preexisting conditions

A preexisting condition (i.e., a disorder present before the AE reporting period started and noted on the pretreatment medical history/physical examination form) should not be reported as an AE unless the condition worsens, or episodes increase in frequency during the AE reporting period.

Procedures

Diagnostic and therapeutic non-invasive and invasive procedures, such as surgery, should not be reported as AEs. However, the medical condition for which the procedure was performed should be reported if it meets the definition of an AE. For example, an acute appendicitis that begins during the AE reporting period should be reported as the AE and the resulting appendectomy entered in the comments section of the eCRF.

Lack of efficacy

“Lack of efficacy” or “expected pharmacological effect has not been reached” will not be reported as an AE or SAE. However, failure of pharmacologic action or therapeutic benefit shall be recorded as an AE when they associated with a SAE or Serious outcome.

Serious adverse event (SAE)

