6.5.5.1.3 Eliciting and recording adverse event information

The investigator is to record all directly observed AEs, and all AEs spontaneously reported by the patient, in the eCRF using concise medical terminology. In addition, each patient will be questioned about AEs at each clinic visit following initiation of treatment

When possible and appropriate, a diagnosis rather than individual signs and symptoms shall be recorded. The investigator is responsible for obtaining sufficient information to determine seriousness, causality, and outcome of each AE.

Severity assessment

The investigator will use the adjectives MILD, MODERATE, or SEVERE to describe the maximum severity of the AE. For the purpose of consistency, these severity grades are defined as follows:

MILD	Does not interfere with patient's usual function
MODERATE	Interferes to some extent with patient's usual function
SEVERE	Interferes significantly with patient's usual function

Note the distinction between the gravity (seriousness) and the severity of an AE. **Severe** is a measure of intensity; thus, a **severe** reaction is not necessarily a **serious** reaction. For example, a headache may be severe in intensity, but would not be classified as serious unless it met one of the criteria for serious events listed above.

If the intensity of an AE worsens during the study, only the worst intensity should be reported on the AE page. If the AE lessens in intensity, no change in the severity is required.

Events occurring during the screening period (i.e. after signature of informed consent up to IMP initiation) are considered medical history. If it worsens after IMP initiation or during the follow-up period, an AE form must be entered with the appropriated intensity.

Causality assessment

For each AE, the investigator must make a causality assessment to determine if there is a reasonable possibility that the IMP caused the AE. The AE is assessed as related or not related to

the IMP. The determination of the likelihood that the IMP caused the AE will be provided by an investigator who is a qualified physician.

- Related

An AE that follows a reasonable temporal sequence from administration of the IMP (including the course after withdrawal of the IMP), or for which possible involvement of the IMP cannot be ruled out, although factors other than the IMP, such as underlying diseases, complications, concomitant drugs, and concurrent treatments, may also be responsible.

- Unrelated

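### The SAP's Complete Response rule reads CSF status from adverse events alone, so CSF that is abnormal at entry and stays abnormal can be scored as normal

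*SAP*

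**What the plan says.** **Complete Response, SAP 6.8.2.** The criterion is "No neurological and CSF abnormalities attributed to HLH". The clarification column turns its CSF half into an equation: "No CSF abnormalities = no AE indicative of" CSF abnormalities, footnoted to the preferred terms in Appendix 2. The neurological half needs a normal "neurological assessment by investigator in the neurological examination page", no brain imaging findings and no event suggesting CNS involvement. It does not name the CSF result. The same cell also carries a general line: "All HLH parameters that were abnormal at baseline must be normalized".

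**Partial Response, SAP 6.8.2.** At least three abnormalities, CNS included, must meet the Complete Response criteria. A reactivated patient who enters with three abnormal features needs two to normalise; one who enters with two needs one.

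**HLH Improvement, SAP 6.8.2.** The CNS rule is wider: "Normalization of CNS abnormalities = normal neurological assessment by investigator without findings in brain imaging (Brain MRI/Brain CT/cranial ultrasound), CSF analysis or AEs indicative of" (the sentence ends by naming the two groups of events listed in Appendix 2).

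**SAP 6.12.** The modified definition keeps both CNS wordings unchanged.

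**Event recording.** AE recording starts at the first dose (Protocol 6.5.5.1.2). Protocol 6.5.5.1.3 adds: "Events occurring during the screening period (i.e. after signature of informed consent up to IMP initiation) are considered medical history". Under Protocol 6.5.5.1.1 a pre-existing condition "should not be reported as an AE unless the condition worsens, or episodes increase in frequency during the AE reporting period".

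**CSF data.** Lumbar puncture is done at screening when CNS involvement is suspected and repeated to follow an abnormal result (Protocol 6.5.7.8). The CRF holds the CSF results and their clinical significance (SAP 6.10.2).

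**The concern.** CNS disease is not among the exclusion criteria (Protocol 6.3.2), and intrathecal therapy may be running at entry (Protocol 6.4.5.2.2). Patients with abnormal CSF at baseline can therefore be in the analysis set. For them, absence of an AE does not mean that the CSF is normal: the recording rules tend to keep unchanged disease out of the AE data.

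Within one table, the strictest category then has the weaker CSF test. At one visit a patient could pass the CNS item for Complete Response and fail it for HLH Improvement, the lowest responding category. What is at stake is the Complete Response percentage, which has its own exact confidence interval, and in some patients the Overall Response classification and the two time measures built on the same algorithm.

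**Working it through.** The plan states no figure on this point, so the check is a trace of the rules, followed by simple arithmetic for scale.

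**Step 1. Does persisting CSF disease produce an AE?** CSF abnormal at screening → medical history (Protocol 6.5.5.1.3) → pre-existing condition, not reported unless it worsens or recurs more often (Protocol 6.5.5.1.1) → in general no Appendix 2 event. The same holds if the CSF improves without becoming normal.

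**Step 2. How does each row score that patient?**
- Complete Response: no Appendix 2 event, so the CSF item is met.
- HLH Improvement: the patient must be "without findings in brain imaging (Brain MRI/Brain CT/cranial ultrasound), CSF analysis or AEs indicative of" CNS or CSF disease. The CSF analysis still shows a finding, so CNS is not normalised.

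**Step 3. Who is exposed?** The neurological half of the Complete Response criterion still applies. A false normal gets through only if the neurological examination is normal, imaging shows nothing and there is no CNS event, that is, CSF-only disease.

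**Step 4. Does the category change?** Assume that baseline CNS status is taken from CSF results, that CSF is still abnormal at assessment, and that there is no organ-failure event or sCD25 worsening. Under SAP 6.8.2:

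| Patient | As written | One CSF-based rule | Overall Response |
|---|---|---|---|
| A. Not reactivated; CSF plus three other abnormalities; the three normalise | Complete Response (4 of 4) | Partial Response (3 normalised) | Unchanged |
| B. Reactivated; CSF plus one other; the other unchanged | Partial Response (1 of 2) | No Response (0 of 2; HLH Improvement needs more than 50% change in both) | Changes |
| C. Not reactivated; CSF plus three others; two normalise, the third is unchanged | Partial Response (3 counted) | No Response (2 counted, 3 needed) | Changes |

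In A the CNS item does not decide responder status; in B and C it does.

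The SAP does not say how baseline CNS status is set. If the AE rule were used at baseline too, CSF-only disease would not count as an abnormality. It could not then be counted as normalised for Partial Response, so B and C would not arise in this form.

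**Step 5. Scale.** Planned N is 10 to 18 (Protocol 6.1). One patient whose category changes is worth 1/10 = 10.0 points or 1/18 = 5.6 points.

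Exact (Clopper-Pearson) limits, the method named in SAP 6.8.2, were computed from beta quantiles. As a check, 27/45 gives 44.3% to 74.3%, matching Protocol 4.1.1.3.2. With an assumed rate near 60%, for illustration only:
- N = 10: 6/10 = 60.0% (26.2 to 87.8) becomes 5/10 = 50.0% (18.7 to 81.3).
- N = 18: 11/18 = 61.1% (35.7 to 82.7) becomes 10/18 = 55.6% (30.8 to 78.5).

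**The case against.** **The general line already covers this.** Abnormal baseline parameters must normalise, and the only place the table spells out CNS normalisation includes the CSF analysis. Read together, entry CSF would have to become normal for Complete Response. This is good evidence of intent. It does not repair the rule, because the Complete Response row has its own CSF equation and the wider wording sits in another row. A programmer following the row literally would not use the CSF result.

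**The abnormality could be reported as an AE.** Protocol 6.5.5.1.1 also makes an abnormal test finding an AE if it is clinically significant or leads to intervention. No text says which rule prevails for a pre-existing finding, and no text names CSF. This stands in part: the step from entry disease to no AE holds generally, not always, and the score would depend on site reporting habits.

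**Most false complete responders are still responders.** This stands, as patient A shows. A reader might infer that every patient with persisting abnormal CSF moves the Overall Response rate, and multiply 5.6 or 10.0 points by an assumed count. The documents support neither the count nor the assumption that each such patient is decisive.

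**The error can go the other way.** A reader might infer that the AE rule always favours response. It does not. Appendix 2 matches preferred terms without attribution to HLH, so a CSF event from infection would block Complete Response. If AEs also set baseline status, the patient has one fewer abnormality to count as normalised.

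**There are other safeguards.** Assessments behind each response criterion are listed by patient (SAP 6.8.2), CSF data are listed (SAP 6.10.2), and investigator-assessed response is reported separately. No hypothesis is tested and the primary endpoint is safety. This lowers the priority but does not remove the inconsistency.

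**Conclusion.** The point holds as an inconsistency in the response algorithm. Taken literally, the Complete Response rows of SAP 6.8.2 and 6.12 can accept recorded CSF that is still abnormal, against the SAP's own stated intent and against the HLH Improvement rows beside them. It is confined to CSF-only CNS disease that was present at entry and did not worsen.

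The main effect is on the split between Complete Response and the lower categories. Overall Response, time to first response and cumulative duration change only where the CNS item is pivotal and baseline CNS status comes from CSF results. One pivotal patient is worth 10.0 points at N = 10 and 5.6 at N = 18; how many there will be cannot be derived from the documents.

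A reader might infer that patients with clinically evident CNS disease could be labelled complete responders. The text does not support that: an abnormal neurological examination, imaging findings or a CNS event would each stop it. This is a should-fix for a descriptive secondary endpoint.

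**What to change.** Use one CNS/CSF rule in the Complete Response, Partial Response and HLH Improvement rows of SAP 6.8.2 and 6.12, and use the same rule to set baseline CNS status. Suggested wording for the CSF part:

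*No CSF abnormalities = latest available CSF analysis at or before the assessment not recorded as clinically significantly abnormal, and no AE indicative of CSF abnormalities.*

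This relies on the clinical-significance field in SAP 6.10.2. Wording that required the result to be free of abnormality due to HLH would need an attribution field, and that section lists none.

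Also state that abnormal baseline CSF without a later normal result is not counted as normalised, and report how many such patients had no repeat CSF. The count matters because the schedule of events (Protocol Table 3) makes CSF testing after screening conditional on clinical indication, although Protocol 6.5.7.8 asks for follow-up of an abnormal first result.

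Cost: SAP wording and one program change, with no new data collection. Since the algorithm runs after database lock, the text should be settled before then. The downside is that patients with abnormal baseline CSF and no repeat cannot be scored Complete Response, so that percentage may be slightly lower.
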